11.4. Vital Signs, Body Weight, and Height

Vital signs (blood pressure, pulse rate, respiratory rate, and oral temperature), height, and weight will be assessed at the scheduled visits specified in Section 4.6.

A summary table of observed and change from baseline values will be provided at each scheduled visit for the safety population, from baseline at Day 1-15, Month 1, Month 3, Month 6, Month 9 and Month 12/ET. Clinically significant abnormal results, in which unscheduled visits will be included, will be summarized with the frequency tables by sex (male, female), ERT status (ERT naïve, ERT experienced), and overall if feasible.

A by-subject listing will be provided for each vital sign parameter.

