5.6. Justification for Proposed Dose and Regimen in Pediatric Subjects with Fabry Disease

Migalastat has not been studied in pediatric subjects under 16 years of age. Although adolescent subjects with Fabry disease 16 to < 18 years of age were included in Phase 3 studies, the number of adolescent subjects included in those studies was limited. Therefore, simulations have been performed (100 subjects per age group) to select doses that match exposure in pediatric patients to exposure observed in adults receiving migalastat HCl 150 mg QOD. Area under the plasma concentration-time curve over the dosing interval (AUC_{0-t}) at steady-state concentration was selected as the target parameter for dose selection in pediatric subjects because existing safety and tolerability data in adults suggest that increased risk is not expected with increases in C_{max} and that changes in minimum observed plasma concentration (C_{min}) are not likely to affect efficacy given there is likely an indirect relationship between plasma concentrations and efficacy. The aim is to achieve AUC values in pediatric subjects that are similar to those in adults with Fabry disease and with normal renal function who were receiving migalastat HCl 150 mg every other day.

The largest biological factor affecting migalastat plasma clearance (CL/F) is renal function. While many adult patients with Fabry disease have reduced renal function (15% and 42% of subjects in Study AT1001-011 with moderate or mild renal impairment, respectively, based on estimated glomerular filtration rate [eGFR]), pediatric patients with Fabry disease have relatively high values for eGFR (mean, 147 mL/min/1.73 m²) (Hopkin, Bissler et al. 2008).

Body weight also explains variability in the pharmacokinetics of migalastat in individuals < 70 kg, with effects on CL/F, volume of distribution in the central compartment (V2/F), volume of distribution in the peripheral compartment (V3/F), and distribution clearance (Q/F). These effects were incorporated into the dose rationale simulations for pediatric subjects by using the range of weights from the Centers for Disease Control and Prevention weight chart (data on file).

Lastly, there is a very small change in CL/F (15%) and V2/F (31%) in the presence of Fabry disease. This effect was accounted for in the simulations, even though these differences result in exposures that are similar to those reported for healthy subjects.

6. **OBJECTIVES AND PURPOSE**

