8. SELECTION AND WITHDRAWAL OF SUBJECTS

8.1. Number of Subjects

Approximately 20 subjects are planned globally for enrollment in this study. An attempt will be made to enroll subjects of each sex. At least 7 to 10 of these subjects will be aged 12 to < 16 years for a subgroup analysis to be conducted at the end of Stage 1.

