8.2.1. Inclusion Criteria

Subjects must meet all of the following criteria to be considered for enrollment in the study:

- 1. have a parent or legally-authorized representative who is willing and able to provide written informed consent and authorization for use and disclosure of personal health information or research-related health information, and subject provides assent, if applicable provides written informed consent
- 2. male or female, diagnosed with Fabry disease aged between 12 and < 18 years at baseline, and who might benefit from specific treatment for their condition, in the opinion of the investigator
- 3. confirmed, amenable *GLA* variant determined using the migalastat amenability assay

Note: For subjects without a known amenable *GLA* variant, *GLA* genotyping must be performed prior to Visit 2.

Note: For subjects with a *GLA* variant that has not yet been tested in the Migalastat Amenability Assay, amenability testing must be completed before Visit 2.

- 4. weight of \geq 45 kg (99 pounds) at screening
- 5. treatment-naïve or discontinued ERT treatment at least 14 days prior to screening
- 6. have at least one complication (ie, historical or current laboratory abnormality and/or sign/symptom) of Fabry disease, for example:
 - a. corneal whorls
 - b. neuropathic pain and/or acroparesthesia and/or acute crises persisting or recurring at least twice over the previous 3 months or longer, or; requiring management with analgesia
 - c. Fabry disease-related gastrointestinal signs and symptoms (eg, diarrhea, abdominal pain) persisting or recurring at least twice over the previous 3 months or longer
 - d. hypohidrosis (present for at least 3 months)
 - e. LVMi above the normal range for age and sex

- f. rhythm and/or conduction disturbances, for example:
 - episode of tachycardia or bradycardia,
 - arrhythmia, or;
 - abnormal PR, QRS, or QT interval
- g. reduced eGFR (using the Schwartz formula) for age and sex, or hyperfiltration (> 135 ml/min/1.73 m²)
- h. proteinuria or albuminuria in spot urine (early morning preferable) or as determined by the investigator (based on local laboratory results documented in the patient's medical record)
- i. plasma lyso-Gb₃ levels above normal (based on local laboratory results documented in the patient's medical record)
- j. hearing impairment and/or tinnitus
- 7. able to swallow capsules

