11.1. Endpoints

11.1.1. Safety Endpoints

Safety endpoints are as follows:

- incidence of TEAEs, SAEs, and AEs leading to discontinuation of study drug
- changes in clinical laboratory test results from baseline over time
- changes in vital signs from baseline over time
- changes in physical examination findings from baseline over time
- change in body weight and height from baseline over time
- changes in ECG results from baseline over time
- changes in echocardiogram parameters from baseline to Month 12/ET
- change in Tanner stage from baseline to Month 12/ET
- use of concomitant medications

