4.1. Summary of Study Design

This is a Phase 3b, 2-stage, open-label, uncontrolled, multicenter study to evaluate the safety, PK, PD, and efficacy of migalastat treatment in pediatric subjects 12 to < 18 years of age and weighing \ge 45 kg (99 pounds) with Fabry disease and with amenable *GLA* variants. Subjects must be either naïve to enzyme replacement therapy (ERT) or have stopped ERT at least 14 days at the time of screening.

The study will consist of 2 stages. Stage 1 will be a treatment period of approximately 1 month (4 weeks); Stage 2 will be a treatment period of 11 months and a 30-day (untreated) safety follow-up period. There will be no break in treatment between Stages 1 and 2. Prior to Stage 1, there will be a screening period lasting at least 14 days and up to 30 days (or more, if *GLA* genotyping is required). The study will consist of a screening period up to 30 days, a 12-month treatment period, and a 30-day safety follow-up period, for a total of approximately 14 months.

Figure 1: Study Design

Safety assessments include monitoring AEs, clinical laboratory tests, vital signs, physical examinations, body weight and height, 12-lead ECGs, ECHOs, Tanner staging of sexual development, and use of concomitant medications. Sparse blood samples for determination of plasma migalastat concentrations and PK analysis will be collected. The PD biomarker to be evaluated in this study is lyso-Gb₃ levels in plasma. Blood samples will also be collected for exploratory biomarkers.

Efficacy assessments include eGFR, urine protein and albumin levels, ECHO parameters, and subject questionnaires (FABPRO-GI and Pain Questionnaire, PGI-C, FPHPQ, and PedsQLTM). The key ECHO parameter considered for efficacy is LVMi. In addition, ejection fraction, fractional shortening, left ventricular internal diameter end diastole and end systole, midwall fractional shortening, and wall thickness will be assessed. Echocardiograms will be read centrally.

A Data Monitoring Committee (DMC) will operate according to a charter that includes operational and logistical procedures for the DMC. The DMC will monitor and evaluate all available safety data from this study by reviewing summaries of safety data on a regular basis, evaluating risk/benefit where possible, identifying any clinically relevant trends through the study, and assessing whether it is safe for the subject and/or study to continue.

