12.2. Tanner Stage

A summary table of assessment results in Tanner stage will include Baseline, Month 6 and12/ET visits for the safety population by sex (male, female), ERT status (ERT naïve, ERT experienced). A by-subject listing will be presented for each Tanner stage parameter, including public hair development, breast development, and genital development.

13. Interim Analyses

An interim analysis was conducted on Stage 1 data for PK and safety assessments. The details are provided in a separate Interim SAP.

14. Changes from Analysis Planned in Protocol

No changes are planned from the analyses described in the protocol, amendment 1 (10Sep2018), amendment 2 (31Oct2018), Protocol Amendment 3 (22Apr2019), and Protocol Amendment 4 (13Jun2019).

15. Programming Considerations

All TLFs and statistical analyses will be generated using SAS[®] for Windows, Release 9.4 (SAS[®] Institute Inc., Cary, NC, USA). Computer-generated table, listing and figure output will adhere to the following specifications.

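### Height and weight are summarised only as raw change in uncontrolled adolescents, so abnormal growth cannot be told from normal growth, and the Tanner table omits the within-subject change that its endpoint requires

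*SAP*

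**What the plan says.** **Design.** SAP 4.1: "This is a Phase 3b, 2-stage, open-label, uncontrolled, multicenter study". Protocol 8.1: "Approximately 20 subjects are planned globally for enrollment in this study". Subjects are 12 to under 18 years old and are treated for 12 months.

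**Height and weight.** The safety endpoints include "change in body weight and height from baseline over time" (Protocol 11.1.1, repeated in SAP 3.2.3). SAP 11.4 answers with: "A summary table of observed and change from baseline values will be provided at each scheduled visit for the safety population". It adds frequency tables of clinically significant abnormal results, split by sex and prior enzyme replacement therapy (ERT), and a subject listing. BMI is derived for baseline only (SAP 7.2). No growth standard is named for any of these measures.

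**Tanner stage.** The endpoint is "change in Tanner stage from baseline to Month 12/ET" (Protocol 11.1.1, again in SAP 3.2.3). Protocol 11.3.2.2 puts Tanner stages among the measures to be summarised both as actual values and as changes. SAP 12.2 reads: "A summary table of assessment results in Tanner stage will include Baseline", followed by Month 6 and Month 12/ET, split by sex and ERT status, with a subject listing. It names no change or shift table. SAP 6.1 allows change from baseline where appropriate, and SAP 14 declares no departure from the protocol's analyses.

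**Related places.** One example under inclusion criterion 6 is "LVMi above the normal range for age and sex" (Protocol 8.2.1), while SAP 8.2 gives LVMi as observed values and change. Protocol 5.6 drew its range of simulated weights from the "Centers for Disease Control and Prevention weight chart".

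**The concern.** Many subjects in this age range will grow during a year on study whatever the drug does. How much they grow depends on age, sex and pubertal stage, and there is no control arm to show what the same subjects would have gained untreated. A table of mean change in cm and kg therefore has no null value: a positive mean is compatible with normal, slowed or accelerated growth.

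The Tanner problem is different in kind. The endpoint is a within-subject change, but stage counts at each visit are marginal totals. One boy moving from G-3 to G-4 and another from G-4 to G-5 leave the same counts as one moving from G-3 to G-5 while the other stays at G-4.

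Safety is a primary objective of both stages, and Protocol 9.2.2.8 says why Tanner staging is there: a reversible infertility finding in male rats. At stake is whether the report can say anything useful about growth and sexual development.

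**Working it through.** The plan gives no expected growth, SD, margin or power for these endpoints, so there is no figure to reproduce. Its sample-size reasoning concerns PK clearance only. The arithmetic below is an illustration; n is the only input from the documents.

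**1. What raw mean height change would be expected with no drug effect?**

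Inputs: n = 20 (Protocol 8.1). Assumed: a fraction f of subjects still grows at g cm/year and the rest have stopped, with f from 0.3 to 0.7 and g from 3 to 7.

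Mean = f × g. SD = g × √(f(1 − f)). 95% half-width = t(0.975, 19) × SD / √20, with t = 2.093.

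| f | g (cm/year) | Mean (cm) | SD (cm) | 95% half-width (cm) |
|---|---|---|---|---|
| 0.3 | 3 | 0.9 | 1.37 | 0.64 |
| 0.3 | 7 | 2.1 | 3.21 | 1.50 |
| 0.5 | 5 | 2.5 | 2.50 | 1.17 |
| 0.5 | 7 | 3.5 | 3.50 | 1.64 |
| 0.7 | 3 | 2.1 | 1.37 | 0.64 |
| 0.7 | 7 | 4.9 | 3.21 | 1.50 |

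The no-effect mean runs from 0.9 to 4.9 cm, a spread of 4.0 cm from case mix alone. That exceeds the sampling error of 0.6 to 1.6 cm.

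**2. Can the raw mean show a slowing?** Take f = 0.7 and g = 7, and suppose growth in the growers slows by 2 cm. The mean becomes 0.7 × 5 = 3.5 cm. That is also the no-effect mean for f = 0.5 and g = 7. The planned table would show the same number in both cases.

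**3. What would a Z-score add?** If growth follows the reference, the expected mean change in Z is about 0 whatever the age and sex mix. With an assumed height SD of 7 cm:

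- A mean shortfall of 2 cm across all subjects gives −2/7 = −0.29 SD.
- If only the growers slow by 2 cm, the mean shortfall is 0.3 × 2 = 0.6 cm to 0.7 × 2 = 1.4 cm, that is −0.09 to −0.20 SD.
- With an assumed SD of Z change of 0.2 to 0.5, the 95% half-width is 0.09 to 0.23 at n = 20, and 0.14 to 0.36 at n = 10 per sex.

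A general shortfall of 2 cm would stand clear of 0 in the whole group. A slowing confined to the growers would be at the edge of what about 20 subjects can show. The gain is a reference point rather than high sensitivity.

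**4. Tanner: the places set side by side.**

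| Place | Content |
|---|---|
| Protocol 11.1.1, SAP 3.2.3 | Endpoint is a change |
| Protocol 11.3.2.2 | Actual values and changes from baseline |
| SAP 12.2 | Results by visit, sex and ERT status; listing; no change or shift table |
| SAP 14 | No change from the protocol's analyses |

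The SAP specifies shift tables for laboratory tests (11.3) and ECG interpretation (11.6), but none here. SAP 12.2 falls short of both the endpoint and the protocol's method, and SAP 14 does not acknowledge it.

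**The case against.** The strongest reply is that little is lost. The analyses are descriptive, about 20 subjects are listed individually, and the inputs for any later Z-score are collected. SAP 11.4 also tabulates clinically significant abnormal results, and a data monitoring committee reviews safety regularly. The age and sex mix will be reported, so a reader could narrow the 4.0 cm range. Much of this stands: the fault lies in the planned summaries, not in the data. But a listing leaves the comparison to the reader, no criterion for an abnormal height is given, and neither document supplies the growth standard that would turn ages into an expected gain.

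A reader might infer more than the documents support:

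- *That better analysis would isolate a drug effect on growth.* Standardising removes expected growth. Without a control it cannot separate drug from Fabry disease, which is a limit of the design.
- *That Tanner change cannot be seen at all.* The by-subject listing shows it, and SAP 6.1 leaves room for a change summary. The gap is a missing table and a mismatch with the protocol.
- *That slowed growth would be reported as absence of a signal.* No rule in either document reads a positive mean that way, and neither says height and weight were included to detect slowing.
- *That LVMi is handled as a raw growth measure.* It is already an index, by a method not stated. It is the key echocardiographic efficacy parameter, and Protocol 11.3.2.2 leaves it out of the safety summaries. The missing age and sex standard makes an efficacy change harder to read; it is not a growth-safety gap. No section says the central reader supplies a normed value.
- *That Protocol 5.6 already provides the growth reference.* It cites a weight chart used as simulation input, not a standard for height or BMI outcomes.

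Z-scores have a weakness of their own. Entry requires at least 45 kg, so the youngest subjects are selected for size. If they are also early maturers, their height Z-score could drift down without any drug effect.

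**Conclusion.** The point holds for the planned summaries. Raw change in height and weight cannot distinguish abnormal from normal growth in this uncontrolled adolescent group, and SAP 12.2 does not deliver the within-subject Tanner change that the endpoint and Protocol 11.3.2.2 call for.

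The size for height, a no-effect mean of roughly 1 to 5 cm, rests wholly on assumed growth fractions and rates. The Z-score figures rest on an assumed height SD and SD of change. The Tanner finding needs no outside assumption.

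This is a gap worth closing before database lock. It does not affect eligibility, dosing, data collection or the PK objective.

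**What to change.** 1. **SAP 11.4:** derive age- and sex-specific Z-scores for height, weight and BMI from a growth reference that the SAP names. Summarise their change from baseline by visit, beside the raw values.
2. **SAP 12.2:** add a Tanner shift table by sex, from baseline to Month 6 and to Month 12/ET, for each Tanner parameter. Reconcile the section with SAP 3.2.3 and Protocol 11.3.2.2.
3. **SAP 8.2, optional:** add an age- and sex-standardised LVMi as a secondary efficacy display, if the central reader's data or a named reference allow it.
4. **Interpretation:** state that these results are descriptive and cannot separate drug from disease effects. State also that Z-score change may drift with pubertal timing and the 45 kg entry limit, so it should be read with the Tanner shifts.

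The cost is a few derived variables and tables. Birth date and sex (Protocol 9.2.1) and height, weight and Tanner stage (Protocol Table 3) are already collected, so no visit or procedure is added.

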11.5. Echocardiography

For categorical echocardiography results, an observed summary table will be provided by each parameter and visit in safety population. Scheduled visits will be included for by-visit summary tables.

Clinically significant abnormal assessments for each parameter will be summarized with frequency tables by sex (male, female), ERT status (ERT naïve, ERT experienced), and overall if feasible. Unscheduled visits will be included. Clinically significant abnormal values will be collected from investigator assessment on the CRF page.

11.6. ECG

A summary table of observed and change from baseline values in ECG results will be provided at each scheduled visit for the safety population. A summary table displaying shifts from baseline to worst post-baseline interpretation assessment (including unscheduled assessments as applicable) will be provided by sex (male, female), ERT status (ERT naïve, ERT experienced), and overall if feasible.

A by-subject listing will be provided, including each ECG parameter: heart rate (beats per minute [bpm]), RR interval [msec], PR interval [msec], QRS interval [msec], QT interval mean [msec], QTc (QTcF or QTcB) [msec] and interpretation. QTc = corrected QT interval, QTcF = corrected QT interval with Fridericia's formula, and QTcB = corrected QT interval with Bazett's formula.

12. Reference List

Online source for PedsQL[™] scoring:

http://www.lsebn.nhs.uk/website/X13911/files/20%20scoring_PedsQL_v13[1].pdf

12.1. Physical Examination

Complete physical examination, including HEENT (Head, Eyes, Ears, Neck and Throat), Respiratory, Cardiovascular, Dermatological, Lymph Nodes, Gastrointestinal, Neurological, Thyroid, Musculoskeletal and other assessments, will be conducted at baseline and Month 3, 6, and 12/ET visits. A categorical summary table will be provided of the physical examination findings at each scheduled visit for the safety population by sex (male, female), ERT status (ERT naïve, ERT experienced), and overall if feasible. A by-subject listing will be presented for each body system.

Brief physical examination will be summarized at Day 15-30, Month 1 and 9 visits. A by-subject listing will also be presented.

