11.3.2.2. Safety Analyses

Adverse events will be coded using the Medical Dictionary for Regulatory Activities (MedDRA) and summarized by system organ class and preferred term. Summaries will be provided for TEAEs, TEAEs by severity, and TEAEs by relationship to study drug as well as deaths, SAEs, and TEAEs leading to discontinuation of study treatment. Listings will also be provided for SAEs and TEAEs leading to discontinuation of study treatment.

Actual values and changes from baseline for clinical laboratory test results, vital signs, body weight and height, ECG parameters, echocardiogram parameters (other than LVMi) and Tanner stages will be summarized using descriptive statistics. Shift tables will also be provided for clinical laboratory tests and ECG results. Physical examination findings will be summarized by body system.

Concomitant medications will be coded using the World Health Organization (WHO) Drug Dictionary and will be summarized by Anatomical-Therapeutic-Chemical classification.

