3.2.3. Safety Endpoints

Safety endpoints are as follows:

- incidence of treatment-emergent adverse events (TEAEs), Serious Adverse Events (SAEs), and adverse events (AEs) leading to discontinuation of study drug
- changes in clinical laboratory test results from baseline over time
- changes in vital signs from baseline over time
- changes in physical examination findings from baseline over time
- changes in body weight and height from baseline over time
- changes in 12-lead electrocardiogram (ECG) results from baseline over time
- changes in ECHO parameters from baseline to Month 12/ET
- change in Tanner stage from baseline to Month 12/ET
- use of concomitant medications

[figure not shown]
4. Study Design

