6.1. General Summary Table and Individual Subject Data Listing Considerations

Summary tables and listings will have text (eg, headers or footers) providing explanatory notes that cover, as appropriate: date of data extraction, date of output generation, Statistical Analysis System (SAS[®]) program name, and any other output-specific details that require further elaboration.

The descriptive summary statistics will be prepared for baseline, each visit, and change from baseline to each visit (if appropriate).

Row entries in post text tables are made only if data exist for at least one subject (eg, a row with all zeroes will not appear). The only exception to this rule applies to tables that summarize the study termination status of subjects (eg, reasons for not completing the study). In this case, zeroes will appear for study termination reasons that no subject satisfied. The summary tables will clearly indicate the number of subjects to which the data apply and data that is unknown or not performed will be distinguished from missing data. All data collected will be reported in data listings.

Missing dates will be imputed as described in Section 6.7. Missing AE intensity and relationship will be imputed as described in Section 6.7.2. No other missing data imputation will be performed. When imputed or derived data are included in the individual subject data listings, they will be flagged.

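### The physical examination endpoint is change from baseline, but the planned tables count findings visit by visit and so do not show within-subject change (minor; listings and adverse event tables cover most of the gap)

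*SAP*

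**What the plan says.** The endpoint, in the protocol synopsis, Protocol 11.1.1 and SAP 3.2.3, is "changes in physical examination findings from baseline over time". It sits under the safety objective, which is one of the two primary objectives of Stage 1 and the only primary objective of Stage 2.

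The analysis text is shorter. Protocol 11.3.2.2 states: "Physical examination findings will be summarized by body system". SAP 12.1 covers the complete examination (baseline, Months 3, 6 and 12/ET) with this sentence: "A categorical summary table will be provided of the physical examination findings at each scheduled visit for the safety population", split by sex, ERT status and overall. For the short examination it adds: "Brief physical examination will be summarized at Day 15-30, Month 1 and 9 visits". It also plans listings: "A by-subject listing will be presented for each body system", and one for the brief examination.

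Elsewhere the plan does compare baseline with later results. Protocol 11.3.2.2 says: "Shift tables will also be provided for clinical laboratory tests and ECG results". SAP 11.3 plans shifts for laboratory values, and SAP 11.6 plans for ECG: "A summary table displaying shifts from baseline to worst post-baseline interpretation assessment".

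**The concern.** A count of subjects with a given finding at each visit is a marginal summary. The endpoint concerns how each subject's findings move relative to that subject's own baseline. Equal counts at baseline and Month 12 are compatible with nobody changing, or with some subjects resolving while others become abnormal.

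Offsetting is conceivable here. Every subject must have at least one past or present Fabry complication to enter, and Protocol 5.4 names neuropathic pain and skin findings among the common paediatric manifestations. Some subjects may therefore be abnormal at baseline in the body systems of interest, although the documents give no rate and the entry criterion can be met by history or a laboratory result alone. The study has no control arm, so within-subject comparison with baseline is the natural evidence for this endpoint. As planned, a reader of the summary tables could not tell how many subjects developed a new finding on drug.

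**Working it through.** The plan gives no figure on this point, so there is none to reproduce. The check has two parts.

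**1. Does any planned table link baseline to a later visit for this endpoint?**

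- SAP 12.1, complete examination: findings by visit. No link.
- SAP 12.1, brief examination: summary by visit. No link.
- Protocol 11.3.2.2: summary by body system. Shift tables are named for laboratory tests and ECG, not for physical examination.
- SAP 6.1 allows a change-from-baseline summary where appropriate, but SAP 6.6.1.4 defines change as the later value minus the baseline value. A subtraction has no meaning for a categorical finding, so this general text does not fill the gap.
- SAP 6.5 already defines baseline for all safety data, so nothing in the definitions stands in the way of a linked table.

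**2. What can by-visit counts say about new abnormalities?**

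Let N be the number of subjects examined at both visits, b the number abnormal in one body system at baseline, and m the number abnormal at the later visit. The number newly abnormal (normal at baseline, abnormal later) must lie between

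- lower bound: max(0, m − b)
- upper bound: min(m, N − b)

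Inputs: N = 20, from the approximate planned enrolment in Protocol 8.1, taking all 20 as examined at both visits. The values of b and m are assumptions, because the documents give no rates.

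| b | m | Lower bound | Upper bound | Upper bound among subjects normal at baseline |
|---|---|---|---|---|
| 4 | 4 | 0 | min(4, 16) = 4 | 4/16 = 25% |
| 6 | 6 | 0 | min(6, 14) = 6 | 6/14 = 43% |
| 8 | 8 | 0 | min(8, 12) = 8 | 8/12 = 67% |
| 8 | 6 | max(0, −2) = 0 | min(6, 12) = 6 | 6/12 = 50% |

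For b = m = 6, the two extremes are:

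- no movement: 6 stay abnormal and 14 stay normal;
- full crossover: 6 resolve, 6 become abnormal and 8 stay normal.

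Both give 6 abnormal and 14 normal at each visit, so the planned table is identical. The last row shows that even a fall in the count does not rule out new findings. A net rise is visible: if m exceeds b, at least m − b subjects must be new.

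The upper bounds need every baseline-abnormal subject to resolve (in the last row, all 8 resolve and 6 others become abnormal). They show what the table cannot exclude. They do not predict what will happen.

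**The case against.** The strongest reply is that little is lost. Protocol 10.1.1 counts as adverse events new signs and symptoms, worsening of existing conditions, and examination changes that the investigator considers clinically significant. Those starting after the first dose are treatment-emergent, and SAP 11.2 tabulates them by organ class, preferred term and maximum severity. A clinically important new finding therefore does reach a summary table, already judged against the subject's earlier state. The remaining changes are in the by-subject listings, which are readable with about 20 subjects. The analysis is descriptive, with no decision rule attached. This stands, and it makes the point minor. A reader might infer that new abnormalities would disappear from the report; the documents do not support that.

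A second reply is that the SAP follows the protocol. That is also right. Both documents have the same mismatch between endpoint and analysis, and the SAP does not depart from what Protocol 11.3.2.2 asks for.

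Nor is physical examination a lone exception. A reader who sees the laboratory and ECG shift tables might infer that it was singled out, but Tanner stage (SAP 12.2) and categorical echocardiography (SAP 11.5) are also tabulated by visit only.

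A third reply is that a table showing baseline and each visit does describe change over time at group level. It does, but only as net change. The counts cannot separate new findings from resolved ones.

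**Conclusion.** The point holds as a minor one. The endpoint is change from baseline, and no planned table shows within-subject change in physical examination findings. With 20 subjects and an assumed 6 abnormal at both visits, the planned table cannot distinguish 0 from 6 newly abnormal subjects; with 4 or 8 assumed, the upper limit is 4 or 8. These figures rest on assumed counts and full follow-up. A reader might take 43% as a likely rate of hidden new findings, but nothing in the documents supports crossover on that scale.

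The gap is confined to the summary tables, and within them to changes not judged clinically significant. Significant changes appear in the treatment-emergent tables, and everything recorded is in the listings.

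**What to change.** Add to SAP 12.1, in substance:

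> For each body system, a shift table using the examination result categories collected on the eCRF will be presented from baseline to each complete examination and to the worst post-baseline result. The number of subjects newly abnormal among those normal at baseline will be reported. Brief examinations will contribute to the worst post-baseline result only for skin, lungs, cardiovascular system and abdomen.

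The reference to the eCRF is needed because SAP 12.1 does not define the categories. The restriction on brief examinations follows Protocol 9.2.2.4: those four areas are always examined, while others are examined only when clinically indicated, so including them would mix routine with selectively performed assessments.

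The cost is one extra table from data already collected, built in the way the SAP already uses for laboratory tests and ECG. One limit remains: a normal/abnormal shift will not show worsening in subjects who are already abnormal at baseline. That information stays in the listings and the adverse event tables.
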